## **10.2. Deaths, Serious Adverse Events and Other Significant Adverse Events**

### **10.2.1. Deaths**

The AE listing will include all AEs, including deaths, regardless of causality; one of the columns in the listing will specify whether the AE was fatal.

### **10.2.2. Serious Adverse Events**

The AE listing will include all AEs, including SAEs; one of the columns in the listing will specify whether the AE was an SAE.

### **10.2.3. Adverse Events Leading to Withdrawal from the Study**

The AE listing will include all AEs, including AEs leading to withdrawal from the study; one of the columns in the listing will specify whether the AE led to withdrawal from the study.

### **10.2.4. Adverse Events Leading to Discontinuation of Study Medication**

The AE listing will include all AEs, including AEs leading to discontinuation of study medication; one of the columns in the listing will specify whether the AE led to discontinuation of study medication.

## **10.3. Subjective Ocular Tolerability**

Results from the subjective ocular tolerability assessment, measured on a 4-point scale, will be summarized descriptively using counts and percentages for each treatment group at the 0 hour time point for each visit. Additionally, the categories “No Discomfort” and “Mild Discomfort” will be pooled into a single category and summarized descriptively, as will the categories “Moderate Discomfort” and “Severe Discomfort”.

Treatments will be compared for the two pooled categories using a Fisher’s exact test for Nyxol vs. Placebo for Stage 1 time points, and Nyxol + LDP vs. Nyxol + LDP vehicle, Placebo + LDP, and Placebo + LDP vehicle for Stage 2 time points. Separate summaries will be created for the study eye and the fellow eye.

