#### Safety Results From the VEGA-1 Study:

Nyxol, when administered with LDP as adjunctive therapy or as a single agent, was well tolerated in this study. Fifty treatment-emergent adverse events (TEAEs) were reported in 15 subjects (34.1%) treated with Nyxol + LDP, 4 TEAEs were reported in 2 subjects (4.4%) treated with placebo alone, 18 TEAEs were reported in 6 subjects (20.0%) treated with Nyxol alone, and 13 TEAEs were reported in 6 subjects (19.4%) treated with placebo + LDP. All subjects experienced mild TEAEs except for 3 subjects: 1 in the placebo alone arm and 2 in the Nyxol + LDP arm. All subjects had TEAEs that were considered possibly, probably, or definitely related to treatment, except for 2 subjects: 1 in the placebo alone arm had an unrelated TEAE and 1 in the Nyxol + LDP arm had a TEAE of unknown relatedness. One subject in the Nyxol + LDP arm had 2 TEAEs (mild conjunctival hyperemia and mild eye irritation) leading both to study medication discontinuation and withdrawal from the study. No subjects had any serious TEAEs, and no subjects died during the study.

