#### Safety:

Safety measures are AEs, ocular tolerability, intraocular pressure (IOP), BCDVA, biomicroscopy, ophthalmoscopy, HR and BP, and subject questionnaire. Urine pregnancy tests for females of childbearing potential will also be conducted.

Measurements:

- Biomicroscopy, ophthalmoscopy, and HR and BP measured in accordance with the site's standard practice
- Ocular tolerability will be measured on a 4-point scale (0-3)
- Intraocular pressure will be measured with a Tono-Pen or Goldmann Applanation tonometry
- Subject questionnaire will be completed by the subject (Appendix 5 and Appendix 6)

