## 9. ASSESSMENT OF SAFETY

#### 9.1. Specification of Safety Parameters

The primary safety measures are subject-evaluated ocular tolerability and AEs. Other safety measures include biomicroscopy, ophthalmoscopy, BCDVA, IOP, subject questionnaire, and systemic safety (as measured by HR and BP). Urine pregnancy tests for females of childbearing potential will also be conducted.

The assessment of safety will be evaluated by:

- Ocular tolerability
- Biomicroscopy of the anterior segment including evaluation of lids, lashes, cornea, conjunctiva, iris, lens, and anterior chamber. Following topical fluorescein administration, the integrity of the cornea should be evaluated by fluorescein staining
- Ophthalmoscopy (direct or indirect) without dilation to evaluate the vitreous and posterior pole
- Best-corrected distance VA
- Intraocular pressure performed with a Tono-Pen or Goldmann Applanation tonometry
- Subject questionnaire
- Heart rate and BP (as per the site's normal equipment and procedures)
- Adverse events

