## **7.4. Planned Study Analyses**

### **7.4.1. Statistical Summaries: Descriptive and Inferential**

Categories for data presentation and analysis will consist of each treatment group: Nyxol and placebo for Stage 1, and Nyxol + LDP, Nyxol + LDP vehicle, Placebo + LDP, and Placebo + LDP vehicle for Stage 2.

All statistical tests will be two-sided and a difference resulting in a p-value of less than or equal to 0.05 will be considered statistically significant. The p-values for the analysis of secondary efficacy endpoints and safety endpoints will be considered descriptive, unless the endpoint is used for the hierarchical testing method. All p-values will be rounded to and displayed in four decimals. If a p-value less than 0.0001 occurs, it will be shown in tables as <0.0001.

Descriptive summaries of variables will be provided where appropriate. For continuous variables, the number of non-missing values (n), mean, standard deviation, median, minimum, and maximum will be tabulated by treatment group. For categorical variables, the counts and proportions of each value will be tabulated by treatment group. Expansion of descriptive table categories within each treatment may occur if such elaborations are thought to be useful.

All study-related data collected will be presented in listings. Study-related data not subject to analysis according to this plan will not appear in any tables or graphs but will be included in the data listings.

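### The only treatment comparison planned for ocular tolerability cannot separate mild discomfort from none; a comparison that can should be added beside it

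*SAP*

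**What the plan says.** Protocol 9.1 gives the measure its standing: "The primary safety measures are subject-evaluated ocular tolerability and AEs". Protocol 5.1 (Safety) has it scored on four levels, 0 to 3.

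SAP 10.3 does three things with the score:

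1. The four levels are reported in full; they "will be summarized descriptively using counts and percentages for each treatment group at the 0 hour time point for each visit".
2. No Discomfort and Mild Discomfort "will be pooled into a single category and summarized descriptively", and Moderate is likewise merged with Severe.
3. "Treatments will be compared for the two pooled categories using a" Fisher's exact test. The contrasts are Nyxol vs placebo in Stage 1, and Nyxol + LDP vs each of the other three arms in Stage 2. Study eye and fellow eye are summarised separately.

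No test of the four-level score, and none of any versus no discomfort, appears in SAP 10.3. The section shows no redaction and gives no reason for the cut-point.

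SAP 7.4.1 sets the level and status of the p-values: "All statistical tests will be two-sided and a difference resulting in a p-value of less than or equal to 0.05" counts as significant, but "The p-values for the analysis of secondary efficacy endpoints and safety endpoints will be considered descriptive" unless the endpoint is in the testing hierarchy.

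**The concern.** The pooled test sees each subject only as moderate/severe or not. Moving any number of subjects from no discomfort to mild discomfort leaves the 2x2 table, and so the p-value, unchanged. That follows from the construction and needs no assumption about the drug.

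It matters if the treatments' effect on comfort is mainly mild. The documents contain no earlier results on this discomfort scale. What they do contain is adverse-event severity from the sponsor's Phase 2 study (Protocol 3.2): "All subjects experienced mild TEAEs except for 3 subjects: 1 in the placebo alone arm and 2 in the Nyxol + LDP arm". If discomfort has a similar severity mix, the one p-value attached to a primary safety measure is computed on a small remainder of the events. It would probably be non-significant while the adjacent counts show a clear difference. A reader of the p-value alone could take it as evidence of comfort.

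**Working it through.** **Inputs.** Arm sizes are about 160 per group in Stage 1 and 80 in Stage 2 (Protocol 5). The test is two-sided at 0.05 (SAP 7.4.1). The plan states no power or expected rate for tolerability, so there is no planned figure to reproduce. The nearest figures are the Phase 2 rates of any TEAE (Protocol 3.2). The arm sizes below are inferred from the printed percentages.

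| Phase 2 arm | Any TEAE | Printed % | Not mild |
|---|---|---|---|
| Nyxol + LDP | 15/44 | 34.1 | 2 |
| Placebo alone | 2/45 | 4.4 | 1 |
| Nyxol alone | 6/30 | 20.0 | 0 |
| Placebo + LDP | 6/31 | 19.4 | 0 |

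Subjects with any TEAE: 15 + 2 + 6 + 6 = 29. Mild only: 29 − 3 = 26, and 26/29 = 90%.

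**What the cut does to the Phase 2 counts** (Nyxol + LDP vs placebo alone, Fisher's exact test):
- any TEAE, 15/44 vs 2/45: p = 0.0004
- not mild, 2/44 vs 1/45: p = 0.62

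**Power.** For n per arm and true rates p1 and p2, exact power is the sum of Bin(x; n, p1) × Bin(y; n, p2) over all (x, y) whose two-sided Fisher p-value is at most 0.05. With the Phase 2 rates standing in for discomfort rates, at 80 per arm:

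| Contrast for Nyxol + LDP | Any vs none | Pooled split |
|---|---|---|
| vs placebo + LDP vehicle | 34.1% vs 4.4%: 99.9% | 4.5% vs 2.2%: 3.6% |
| vs Nyxol + LDP vehicle | 34.1% vs 20.0%: 45% | 4.5% vs 0%: 16% |
| vs placebo + LDP | 34.1% vs 19.4%: 49% | 4.5% vs 0%: 16% |

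The reason for the 3.6% is plain from the counts. With 80 per arm and 5 moderate/severe subjects in all, even a 5–0 split gives p = 2 × C(80,5)/C(160,5) = 0.059. Six are needed: 2 × C(80,6)/C(160,6) = 0.028. The proxy rates predict only 80 × (2/44 + 1/45) = 5.4 such subjects across both arms.

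**Sensitivity to the mild share.** Keep any discomfort at 34.1% vs 4.4% and give both arms the same mild share m. The pooled rates are then 34.1% × (1 − m) and 4.4% × (1 − m). At 80 per arm:

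| Mild share m | 50% | 70% | 80% | 90% | 95% |
|---|---|---|---|---|---|
| Pooled power | 89% | 58% | 30% | 4% | 0.2% |

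**Pooled test against a rank test on all four levels.** These distributions (none/mild/moderate/severe) are assumed, not taken from the documents. Control is 85/13/1.5/0.5%. Pooled power is exact; rank (Wilcoxon with ties) power is by simulation.

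| Active arm | 80 per arm: pooled, rank | 160 per arm: pooled, rank |
|---|---|---|
| 65/30/4/1% | 6%, 84% | 20%, 99% |
| 55/40/4/1% | 6%, 99% | 20%, >99% |
| 80/10/8/2% | 44%, 17% | 83%, 30% |

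The last row is the reverse case, where the difference lies mainly in moderate/severe discomfort; there the pooled test is clearly better.

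**No difference.** With 2% moderate/severe in both arms, the pooled test rejects 1.3% of the time at 160 per arm and 0.2% at 80, against a nominal 5%.

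**The case against.** The strongest reply is that nothing is hidden. SAP 10.3 prints counts and percentages for all four levels by arm, so a rise in mild discomfort would be visible. SAP 10.1 also tabulates adverse events by maximum severity, mild included. Safety p-values are descriptive, no tolerability hypothesis or margin is set, and adverse events, the other primary safety measure, get no test at all. Moderate or severe discomfort is also a legitimate threshold, and the pooled test is the better one when the difference lies there. All of this stands. It limits the point to the p-value, not the report.

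Two stronger readings are tempting, and the documents support neither.

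- A reader might infer that mild discomfort is known to be nearly all of the drug's effect. The 26 of 29 counts subjects by the severity of all TEAEs, pooled over four arms that include placebo. Conjunctival redness, which is not discomfort, is among the most common events (Protocol 3.1). That section also describes severity across the programme as mild to moderate. The mild grade for adverse events rests on disruption of daily activity (Protocol 9.3.1), which is a different instrument.
- A reader might infer that the trial would report no difference in tolerability. The SAP says nothing of the kind, and its own four-level table would contradict such a statement.

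The timing also matters. The comparison uses the 0 hour point of each visit. At Visit 2 that is about 12 hours after the evening dose (Protocol 5), so the contrasts modelled here may not apply to that visit.

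**Conclusion.** The point holds in a limited form. The one treatment comparison planned for a primary safety measure is blind to mild versus no discomfort, and that part is certain. How much is lost depends on an unknown severity mix. With Phase 2 TEAE rates as a proxy, pooled power for Nyxol + LDP against placebo + LDP vehicle at 80 per arm is about 4%, against more than 99% for any versus none. It rises to about 30% if 80% of discomfort is mild and to 89% if half is. Against the two single-agent arms, any versus none would itself reach only 45% to 49%, so it is more sensitive there but not decisive.

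The consequence is a descriptive p-value that could sit at odds with the counts beside it. It does not bias the efficacy results, use alpha or remove safety information from the report. This is a cheap improvement to the plan, not a defect that endangers its conclusions. The documents give no ground for demoting the pooled test or for making another test the main one.

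**What to change.** In SAP 10.3, keep the four-level table and the pooled Fisher test as they are. Add beside them, for the same contrasts and for each eye:

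- a row-mean-score (rank) test on the full 0-3 score;
- the percent of subjects with any discomfort (score of 1 or more) in each arm, with the between-arm difference and its 95% CI.

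State that both additions are descriptive under SAP 7.4.1, and that the p-values are to be read with the four-level counts.

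Cost: a sentence or two in SAP 10.3 and a few extra rows in tables already planned. No new data are needed and no alpha is used. The drawback is one more descriptive p-value per contrast, which may disagree with the pooled one. That disagreement would be informative, because it would show whether a difference lies in mild discomfort or in moderate and severe discomfort.

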# Pilocarpine Hydrochloride

A detailed report of pilocarpine, its product label, properties, and potential risk are provided in the IB (2022).

Pilocarpine hydrochloride (PCH) has been studied in a prior clinical trial by Ocuphire. In addition, there is a recently approved PCH drug at 1.25% and extensive literature on pilocarpine's ability to reduce PD across various concentrations. These pupil-constricting effects, however, are counteracted by a dose-dependent side effect profile, notably browache and stinging in the eye upon topical application of the drug.

In an effort to better characterize an efficacious dose of PCH that would have minimal side effects, Ocuphire conducted an expansive review of the medical literature concerning experiments of various doses of PCH and their effects on PD and side effect profile. Leavitt et al. found that normal pupils constrict with dilute concentrations of 0.25% and 0.125% pilocarpine (1.7 and 0.6 mm, respectively) but constrict insignificantly at concentrations of 0.0313% and 0.0625% (4). These decreases in PD were found to occur within 15 min of dosing, and peak pupil size reduction occurred at 30 to 60 min (4). On the other hand, 2% pilocarpine, although efficacious in decreasing PD by up to 3 mm, caused significant side effects, including worsened visual field and acuity (5).

When considering the effects on PD and the potential side effects of higher doses of pilocarpine, Ocuphire found that a range of 0.3% to 0.6% PCH may provide moderate efficacy with potentially limited side effects. Moreover, based on these data, Ocuphire has shown in its Phase 2 VEGA-1 study that the combination of Nyxol and LDP can have an additive to synergistic effect to produce a long duration of pupil reduction in an optimal range of PDs for treating presbyopia, without causing adverse side effects such as headache, browache, or accommodative spasm.

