# 5. STUDY DESIGN

This is a randomized, double-masked, placebo-controlled, multicenter, Phase 3 study in approximately 320 subjects with presbyopia. The study will be performed in 2 stages, as shown in Appendix 4.

Subjects will be randomized 1:1:1:1 to treatments for both stages at Visit 1 (Screening/Baseline). Treatment 1 assignment in Stage 1 will be maintained for Stage 2. Stage 1 will consist of 2 treatment groups (Nyxol or placebo [ie, Nyxol vehicle]), with approximately 160 subjects in each group. Stage 2 consists of 4 treatment groups (Nyxol + LDP, Nyxol + LDP vehicle, placebo + LDP, and placebo + LDP vehicle), with approximately 80 subjects per treatment group.

In Stage 1, the safety and efficacy of Nyxol as a single agent will be evaluated over the following 1 day and 7 days of daily dosing in the evenings near bedtime, except the evening before Visit 2, when Treatment 1 is dosed as close to 12 hours prior to Time 0 min for that visit. Following Visit 2 (Stage 1 Day 8), subjects will discontinue dosing Treatment 1 for 7 to 14 days (Washout Period). During the Washout Period, subjects will return for Visit 3 (Stage 1 Day  $10 \pm 1$  day) to assess the resolution of drug treatment effects.

During Stage 1, subjects will dose with Treatment 1 (Nyxol or placebo [ie, Nyxol vehicle]) in the evenings near bedtime (except for Visit 1 [Stage 1 Day 1], when the subject is dosed during the day at the study site).

Measurements will be made at multiple visits and timepoints, and analysis will consist of comparison across the 2 arms:

- Nyxol
- Placebo

# Stage 2: Dosing of Treatments 1 and 2

Visit 4 (Stage 2 Day 1) is the start of Stage 2. In Stage 2, the efficacy and safety of Nyxol + LDP will be evaluated following 1 day and 7 days of dosing, in which Treatment 1 (Nyxol or placebo) is dosed daily in the evenings near bedtime, except the evening before Visits 4 and 5, when Treatment 1 is dosed as close to 12 hours prior to the scheduled time for those visits. Treatment 2 (LDP or LDP vehicle) is dosed daily in the mornings. Treatment 2 will be dosed at the study site at the beginning of Visits 4 and 5 (Stage 2 Days 1 and 8, respectively).

Measurements will be made at multiple visits and timepoints, and analysis will consist of comparison across the 4 arms:

- Nyxol + LDP
- Nyxol + LDP vehicle
- Placebo + LDP
- Placebo + LDP vehicle

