Table 2. Schedule of Events for Stage	Visit 4[a]							Visit	5[a]					
	Stage 2 Day 1 (Day 15 to 22)						Stage 2 Day 8 (7 days after Stage 2 Day 1)							
Time (hr)[b]	12 hr post Treatment 1	0	0.5	1	3	5	8	12 hr post Treatment 1	0	0.5	1	3	5	8
Prior/Concomitant medications	Х							X						
Urine pregnancy test[c]	Х							Х						
HR/BP														Х
Biomicroscopy														Х
IOP[g]														Х
Ophthalmoscopy[h]														Х
AEs	Х													Х
Subject questionnaire[k]					Х							Х		
In-office Treatment 2: LDP or LDP vehicle[i]		Х							Х					
Ocular tolerability[j]		Х							Х					
Treatment 1: Nyxol or placebo and Subject							X							Х
diary dispensed / reviewed[1]							Λ							Λ
Treatment 2: LDP or LDP vehicle and Subject diary dispensed / collected[i]							X							Х

AE, adverse event; BCDVA, best-corrected distance visual acuity; BP, blood pressure; DCNVA, distance-corrected near visual acuity; HR, heart rate; ID, identification; IOP, intraocular pressure; LDP, Low-Dose Pilocarpine; OD, right eye; OS, left eye; PD, pupil diameter; VA, visual acuity.

[a] Time of visits will be scheduled relative to the prior evening's dose of Treatment 1. Visits 4 and 5 will be scheduled such that the 12 hour post-dose assessments on Visits 4 and 5 will occur approximately 12 hours ( $\pm$  1 hour) after the prior evening's dose of Treatment 1.

[b] An additional  $\pm 5$  min is permitted for measurements at 0.5 and 1 hour; an additional  $\pm 10$  min is permitted at 3, 5, and 8 hours for Visits 4 and 5.

[c] Urine pregnancy test is for females of childbearing potential only.

[g] IOP performed with Tono-Pen or Goldmann applanation tonometry.

[h] Direct or indirect ophthalmoscopy performed without dilation. Use of 90 D lens (indirect) is allowed.

[i] Treatment 2: One drop of LDP or LDP vehicle in each eye dosed daily in the mornings beginning on the day after Visit 4 and daily through the day prior to Visit 5. At Visits 4 and 5, subject will be dosed with Treatment 2 at the study site. Subject will bring Treatment 2 kit and diary to Visits 4 and 5 for review and accountability.

[j] Ocular tolerability performed it will be assessed at the beginning of each specified timepoint after dosing at Visits 4 and 5.

[k] Subject questionnaire (Appendix 5 and Appendix 6) will be completed by the subject at specified visits and timepoints.

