## **10. STATISTICS**

#### 10.1. Sample Size

Subjects will be randomized 1:1:1:1 to Nyxol + LDP, Nyxol + LDP vehicle, Placebo + LDP, and Placebo + LDP vehicle respectively. As a result, subjects will be randomized 1:1 to Treatment 1 (Nyxol or placebo).

An additional 20 subjects will be enrolled to account for dropouts, for a total of approximately 320 subjects to be randomized.

A diagram outlining the study design can be found in Appendix 4.

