## 5. STUDY METHODS

### 5.1. General Study Design and Plan

This is a randomized, double-masked, placebo-controlled, multicenter, Phase 3 study in approximately 320 subjects with presbyopia. The study is performed in 2 stages, as described below.

Subjects are randomized 1:1:1:1 to treatments for both stages at Visit 1 (Screening/Baseline). Note that Visit 1 (Screening/Baseline) assessments are recommended to be performed on the same day; however, in instances in which subjects are unable to complete the full day of assessments for Visit 1, subjects may be scheduled to return for the completion of Visit 1 within 1 week of Screening. If Visit 1 is split over 2 separate days, all visit assessments up to and including randomization must occur on the first day, and then the subject should return to complete their post-randomization assessments on the second day.

Stage 1 consists of 2 treatment groups (Nyxol or placebo [ie, Nyxol vehicle]), with approximately 160 subjects in each group. Stage 2 consists of 4 treatment groups (Nyxol + LDP, Nyxol + LDP vehicle, placebo + LDP, and placebo + LDP vehicle), with approximately 80 subjects per treatment group. Treatment assignments for Stage 1 and Stage 2 are assigned at randomization prior to Stage 1.

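### At Visits 4 and 5 subjects rate the Treatment 2 drop, but SAP 10.3 has only one contrast that isolates LDP (about 80 vs 80); a supportive LDP-versus-vehicle estimate stratified by Treatment 1 would use all four arms.

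*SAP*

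**What the plan says.** **What is rated.** Protocol section 5 sets Time 0 at Visits 4 and 5 as the moment of the Treatment 2 drop. Protocol Table 2 marks ocular tolerability at 0 h, and its footnote [j] reads: "Ocular tolerability performed it will be assessed at the beginning of each specified timepoint after dosing at Visits 4 and 5". Footnote [a] of the same table puts the last Treatment 1 dose about 12 hours earlier. The Stage 2 rating is therefore taken just after LDP or LDP vehicle.

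**What is compared.** SAP 10.3 summarizes the 4-point rating by treatment group at 0 hours for each visit. It pools none with mild and moderate with severe, and applies Fisher's exact test to Nyxol against placebo in Stage 1. In Stage 2 the test is applied to "Nyxol + LDP vs. Nyxol + LDP vehicle, Placebo + LDP, and Placebo + LDP vehicle for Stage 2 time points".

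**Status.** Protocol 9.1 states: "The primary safety measures are subject-evaluated ocular tolerability and AEs". SAP 7.4.1 treats p-values for safety endpoints as descriptive. Protocol 3.1 describes pilocarpine's dose-dependent side effects as "notably browache and stinging in the eye upon topical application of the drug", and gives limited side effects as a reason for the low concentration range.

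**Size.** SAP 5.1 plans Stage 2 "with approximately 80 subjects per treatment group". Protocol section 5 plans the two Stage 1 groups "with approximately 160 subjects in each group".

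**The concern.** The four Stage 2 arms form a balanced two-by-two layout of Treatment 1 (Nyxol or placebo) by Treatment 2 (LDP or vehicle). The natural question for a rating made just after the Treatment 2 drop is LDP against its vehicle, and the layout answers it twice, once on Nyxol and once on placebo. SAP 10.3 uses only the first answer.

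Stage 1 is handled differently. There the Treatment 1 groups are compared with each group's two future Treatment 2 assignments combined, so the in-office Treatment 1 drop at Visit 1 is assessed in the full sample. The Treatment 2 drop in Stage 2 is not.

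At stake is the precision with which the trial describes LDP's instillation comfort, on a primary safety measure and for a side effect that the protocol itself names.

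**Working it through.** **1. Reproduce the group sizes.** Protocol 10.1: "Subjects will be randomized 1:1:1:1 to Nyxol + LDP, Nyxol + LDP vehicle, Placebo + LDP, and Placebo + LDP vehicle respectively", "for a total of approximately 320 subjects to be randomized".
- Per Stage 2 arm: 320 / 4 = 80, as stated.
- Per level of one factor: 320 / 2 = 160, as stated for Stage 1.

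**2. What each planned Stage 2 contrast holds fixed.**

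| Nyxol + LDP against | Treatment 1 | Treatment 2 | Isolates LDP? |
|---|---|---|---|
| Nyxol + LDP vehicle | same | differs | yes, 80 vs 80 |
| Placebo + LDP | differs | same | no |
| Placebo + LDP vehicle | differs | differs | no, both drugs change |

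The contrast that isolates LDP uses 80 + 80 = 160 of 320 raters. Placebo + LDP against placebo + LDP vehicle would isolate LDP in the other 160 and is not listed. Both LDP arms against both vehicle arms is 160 vs 160.

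**3. Precision.** The documents give no tolerability rates, so all rates below are assumptions. With 8% moderate/severe on LDP and 2% on vehicle in both Treatment 1 groups, the half-width is 1.96 × √[(p₁q₁ + p₀q₀)/n], where p₁q₁ + p₀q₀ = 0.08 × 0.92 + 0.02 × 0.98 = 0.0932.
- n = 80: 1.96 × √(0.0932/80) = 0.067, or 6.7 points.
- n = 160: 1.96 × √(0.0932/160) = 0.047, or 4.7 points.

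**4. Power under a common LDP effect.** Fisher's exact test, two-sided 0.05, by enumerating both binomials:

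| LDP vs vehicle (assumed) | 80 per group | 160 per group |
|---|---|---|
| 3% vs 1% | 2% | 11% |
| 5% vs 2% | 6% | 20% |
| 8% vs 2% | 26% | 62% |
| 10% vs 3% | 31% | 66% |
| 10% vs 2% | 44% | 83% |

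With 75 and 150 evaluable per group (from the planned 300 evaluable), 8% vs 2% gives 23% and 58%.

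**5. Power if the LDP effect differs by Treatment 1.** Continuity-corrected Mantel-Haenszel test, simulated over two strata of 80 vs 80, with 8% vs 2% in the Nyxol stratum. The planned Nyxol-stratum Fisher test has 26% throughout.

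| Placebo stratum, LDP vs vehicle (assumed) | Stratified power |
|---|---|
| 8% vs 2% | 62% |
| 5% vs 2% | about 40% |
| 3% vs 2% | about 26% |
| 2% vs 2% | about 20% |

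In the last row the excess is 6 points on Nyxol and 0 on placebo. With equal strata the common risk difference then averages to (6 + 0)/2 = 3 points, which understates the excess in Nyxol users.

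**The case against.** Several points against this carry weight.

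- **No data are lost.** A reader might infer that the plan throws away half of the tolerability ratings. It does not: SAP 10.3 tabulates every arm and SAP section 10 lists every subject. Anyone can add the counts. What is absent is a specified estimate with a confidence interval.
- **No formal conclusion depends on these tests.** A reader might also infer that a real LDP excess would go unseen when the Fisher test misses 0.05. Because safety p-values are descriptive, an excess would still show in the four-arm table. The power figures therefore measure information, not the chance of a regulatory finding.
- **The omitted subjects are not wholly unused.** Placebo + LDP vehicle ratings enter the third contrast, which contains the LDP effect mixed with any Nyxol effect. Placebo + LDP ratings enter the second, which holds LDP fixed.
- **The planned contrast matches the objective.** The primary objective concerns LDP as an adjunct to Nyxol, so Nyxol + LDP against Nyxol + LDP vehicle is the directly relevant comfort question. The same three contrasts serve the secondary efficacy endpoints (SAP 9.1.2). It would go too far to conclude that the combined comparison should become the main one: half of its weight comes from subjects not on Nyxol, and its advantage depends on similar LDP effects in both strata. The 12-hour gap since Treatment 1 makes that plausible, but the documents do not establish it.
- **Events may be rare.** Protocol 3.2 reports that in VEGA-1 all but 3 subjects had only mild treatment-emergent events. With rare moderate/severe ratings both analyses are weak, as the first two rows of the power table show.
- **Other capture and redaction.** Stinging can also be recorded as an adverse event, and the planned table list (SAP 12.1) is blacked out and could hold a combined table. The visible text of SAP 10.3, which sets the method, names none.

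These points limit the weight of the concern and rule out replacing the planned contrasts. They do not remove the case for a supportive estimate.

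**Conclusion.** The point holds as a cheap improvement. SAP 10.3 names one contrast that isolates LDP's instillation discomfort, in half of the raters, and leaves the matching comparison on placebo Treatment 1 unmade. With a similar LDP effect in both Treatment 1 groups, using all arms cuts the confidence interval width by a factor of √2; at the assumed 8% vs 2% it also more than doubles power. The gain in power shrinks as the effect in the placebo stratum shrinks, and reverses if there is no excess there. The size rests entirely on assumed rates and on nominal arms of 80. The precision argument stands whatever the status of the p-values; a claim that the plan is invalid or loses data does not.

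**What to change.** Leave the three Stage 2 contrasts in SAP 10.3 as planned. For Visits 4 and 5, add a supportive comparison of the two LDP arms (about 160) with the two LDP vehicle arms (about 160), stratified by Treatment 1, using an exact stratified or Mantel-Haenszel method. Report the common risk difference of moderate/severe discomfort with its 95% CI, and beside it the LDP-minus-vehicle difference within the Nyxol and placebo groups. Produce it separately for study eye and fellow eye, as the section already requires, and label it descriptive.

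The cost is a sentence or two in the SAP and one table; conduct, masking and the testing hierarchy are untouched. The drawback is that the common estimate averages over Treatment 1. The within-group differences make that visible, and the Nyxol-stratum contrast remains the one to read for the combination.
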